# 2 Appendix I: Interim analysis method for estimating full data set characteristics

#### 2.1 Aim

The aim of the simulation is to, at the interim point, be able to estimate the following in the full data set:

- 1) Average number of reported study attacks per patient in the full data set
- 2) The number of patients who will drop out of study (NDO), "drop out" defined here as not having reported at least one study attack by the overall completion of Stage 1. NDO can be subdivided into:
  - a) Participants that will have actively dropped out of, or been exited from, the study by the end of overall completion of Stage 1 and who by the time of dropout has NOT reported at least one study attack ("Intentional dropout")
  - b) Participants that have not actively dropped out or been exited but who at the end of overall completion of Stage 1 has not yet reported a study attack ("Passive dropout")

There will be a number of participants that will have actively dropped out of, or been exited from, the study by the end of overall completion of Stage 1 but who by the time of dropout *have* reported at least one study attack. In the context of the sample size re-estimation, these patients will not count in the dropout percentage since they do contribute data to the end point analysis.

#### 2.2 Method

A time-progressing simulation was implemented in Microsoft Excel, with the following steps:

#### Step 1: Input

Use interim data to calculate the following simulation input:

- The likelihood of a patient reporting an attack in a given week. This is calculated as the total number of reported attacks in the interim data set, divided by the summed number of patient weeks in study at the interim point.
- The likelihood of a patient dropping out of, or being exited from, the study in a given week. This is calculated as the total number of intentional dropouts in the interim data set, divided by the summed number of patient weeks in study at the interim point.

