# 1.2 Study Design

PAREMA1 is a randomized, controlled, double-blinded, parallel-group, group-sequential clinical study randomizing participants to either active or sham treatment, in a 1:1 ratio.

The clinical investigation will randomize at minimum 200 participants and at maximum 240.

In Stage 1 of the trial the participants will treat up to four attacks each. The first treated attack is a training attack and will not be used in the statistical analysis. All attacks reported after the training attacks are study attacks and will be used in the analysis. The reason for discarding the first attack is that it (cf. the pilot trial and post-market data) is not representative of normal use and effectiveness, the user having not yet become accustomed to correct use of the device.

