#### Simulation:

On a week by week basis going forward in time from the interim point, simulate occurrences of dropout and attack reports for each patient, according to the likelihoods in the interim data set. This entails adding new patients to the data set at the time in the future where they are projected to be enrolled.

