#### Output:

At the end of the study simulation (i.e. the overall conclusion of Stage 1), calculate the number of dropouts ( $N_{DO}$ ) and the average number of study attacks reported per patient. Run 20 simulations and average results.

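### One pooled weekly attack probability in SAP Appendix I understates, if patients differ, the share with no study attack, and can set the re-estimated sample size too low when the interim results fall below plan

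*SAP*

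**What the plan says.** SAP Appendix I, Step 1 (Input) sets one value for "The likelihood of a patient reporting an attack in a given week", obtained by a single ratio: "total number of reported attacks in the interim data set, divided by the summed number of patient weeks in study at the interim point". In the simulation step the analyst must then "simulate occurrences of dropout and attack reports for each patient, according to the likelihoods in the interim data set", week by week, adding future patients as they are projected to enrol. No patient-level rate, spread parameter or baseline frequency enters. The weekly dropout likelihood is pooled in the same way: "total number of intentional dropouts in the interim data set, divided by the summed number of patient weeks".

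Section 2.1 (Aim) treats as dropout any patient without usable data, "defined here as not having reported at least one study attack by the overall completion of Stage 1". This includes passive cases: a patient still in the study who "has not yet reported a study attack". SAP 1.2 adds that "The first treated attack is a training attack and will not be used in the statistical analysis", so a patient needs at least two reported attacks to contribute one study attack. The Output step is to "calculate the number of dropouts" and the mean number of study attacks, averaged over 20 runs. SAP 1.4 feeds both into the choice of N_t, together with the observed response rates and intraclass correlation. SAP 1.2 holds N_t between 200 and 240.

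**The concern.** The share of patients with fewer than two reported attacks comes mostly from those who attack, or report, rarely. Giving everyone the average rate removes that group from the simulation.

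The documents themselves expect patients to differ. Protocol 12.1.1 admits anyone with three or more aura attacks in six months and states no upper limit on aura attacks. Protocol 11.4.1 lists baseline attack frequency as a parameter to correlate with outcome. SAP 1.5.1 plans for one, two or three study attacks in equal thirds.

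If the projected no-data share is too low, the re-estimation expects more evaluable patients than will arrive. The power at stake is that for PF2, the endpoint on which Protocol 16.3 bases the re-estimation. AMSP2 has far more room: SAP Table 1 gives it 99.1% at 200 randomized.

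**Working it through.** **Planning figure.** SAP Table 1: 200 × (1 − 0.32) = 136 evaluable, as stated. Take ICC 0.486 (SAP 1.5.1) and two attacks per subject. The design effect is 1 + 0.486 = 1.486, so each arm has 68 × 2 / 1.486 = 91.5 effective attacks. At 12% vs 30% and two-sided 0.048, PF2 power is 85.0%, against 85.5% in the table. The literal 1/2/3 mix has design effect (1 + 2 × 1.486 + 3 × 1.972)/6 = 1.648 and gives 81.1% by formula and 82-88% by simulation. Appendix I states no numerical result to reproduce.

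**Closed form.** Let m be the mean number of attacks in follow-up.
- Common rate: P(fewer than 2) = e^(−m)(1 + m).
- Gamma-distributed rates with shape k (CV = 1/√k): P(fewer than 2) = (k/(k+m))^k × [1 + km/(k+m)].

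At m = 3:
- common rate: e^(−3) × 4 = 19.9%;
- k = 4 (CV 0.5): (4/7)^4 × (1 + 12/7) = 28.9%;
- k = 2 (CV 0.71): (2/5)^2 × (1 + 6/5) = 35.2%.

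At m = 6 the values are 1.7%, 8.7% and 15.6%. The sign reverses only when m is below about 1.

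**Simulation of Stage 1 with Appendix I applied as written.** From the documents: exit at four attacks, six months after the last patient in, interim at the 60th patient with a study attack, and 10% of attacks missing at 2 hours. Assumed: 117 weeks of enrolment, 200 patients, dropout hazard 0.5% per week, and the attack rates and spreads shown. All reported attacks are counted, and patient-weeks stop at exit from Stage 1. N is for 85% PF2 power at 12% vs 30%. Each pair is Appendix I / true.

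| Mean per week | CV | No-study-attack share | N unbounded | N_t after 200-240 | True PF2 power at Appendix I N_t |
|---|---|---|---|---|---|
| 0.04 | 0.5 | 37.5% / 41.7% | 236 / 277 | 236 / 240 | 78.9% |
| 0.04 | 0.71 | 40.3% / 46.4% | 248 / 300 | 240 / 240 | 76.3% |
| 0.06 | 0 | 20.9% / 22.6% | 179 / 196 | 200 / 200 | 85.7% |
| 0.06 | 0.5 | 23.7% / 29.2% | 186 / 217 | 200 / 217 | 82.1% |
| 0.06 | 0.71 | 25.7% / 34.1% | 192 / 234 | 200 / 234 | 79.1% |
| 0.115 | 0 | 8.3% / 9.9% | 149 / 157 | 200 / 200 | 92.5% |
| 0.115 | 0.5 | 9.5% / 14.9% | 151 / 169 | 200 / 200 | 90.5% |
| 0.115 | 0.71 | 11.1% / 19.4% | 155 / 180 | 200 / 200 | 88.6% |

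At 0.12 per week and hazard 0.8%, the shares are 13.2% / 18.2% (CV 0.5) and 16.2% / 26.0% (CV 0.8).

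**What is not due to spread.** With no spread the share is still 1.6-1.7 points low in the table, and about 2.6 points low at hazard 0.8%. The reason is that dropouts without a study attack are divided by all patient-weeks, including those after the first study attack. That is a separate matter. The N columns also differ at CV 0 (179 / 196), mainly because only the mean number of attacks is carried into the power formula. To isolate the share, scale N by (1 − projected)/(1 − true). At 0.06 per week this gives 186 × 0.763/0.708 = 200 for CV 0.5 and 192 × 0.743/0.659 = 216 for CV 0.71. On the share alone, N_t at CV 0.71 is therefore about 16 too low, of the 34 in the table.

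**Effect below plan at the interim.** With 28% vs 12% PF2, 0.12 per week and CV 0.8, two calculations give 200 vs 213 and 211 vs 241 (240 after the cap).

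**The case against.** **The floor.** A reader might multiply 200 by a ratio such as (1 − 0.160)/(1 − 0.255) = 1.13 and infer that N_t is up to 26 patients too low, or that the error fills most of the 40-patient range. The documents do not support this, because the required N does not start at 200. At 0.12 per week with the planned PF2 rates, the calculations put the true need at 157-180 (CV 0.5) and 174-203 (CV 0.8), depending on how missing attacks and the attack distribution are handled. Appendix I gives less, and the floor sets 200 either way to within about 3 patients. This stands.

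**Direction.** It would also be too strong to call the bias downward whatever the terms mean. If reported attacks meant study attacks only, the error would shrink or reverse: at 0.06 per week and CV 0.71 the projection is 39.3% against a true 34.6%. Patient-weeks that ran on into Stage 2 would also lower the rate. SAP 1.7.1 counts the training attack among attacks treated and reported, so counting all attacks is the natural reading, but Appendix I does not say so.

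**Entry criterion.** Three attacks in six months is 3/26 = 0.115 per week, and a gamma distribution with mean 0.12 and CV 0.5-0.8 puts 54-59% of patients below that. With a minimum of 0.03 and mean 0.06, the understatement is 3.5-5.5 points and N_t is 200 vs 204-223. With a minimum of 0.115 and mean 0.2, N_t is 200 either way. This limits the size but does not remove the point. The criterion concerns past attacks, while the simulation needs attacks treated and reported, and Protocol 13.4.1 bars some attacks, such as those not treated within ten minutes. Uneven reporting is itself a difference between patients.

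**Noise.** Assume 30 patients per arm with 1.8 attacks each. The standard error of the interim PF2 difference is then about 9 points, and one standard error either way moves the unbounded N from about 87 to about 811. That is far larger than this bias. But the bias runs one way on the natural reading and can be removed with data already held.

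**Partial credit.** Frequent attackers leave after four attacks, which lowers the pooled rate (0.053 against a true 0.060 at CV 0.71) and offsets part of the error. Appendix I also runs forward from the interim point, so attacks already reported are kept. Each enrolled patient's future rate is still the pooled one.

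**Conclusion.** The point holds conditionally. If attack rates differ between patients and the count includes training attacks, Appendix I understates the share with no study attack and biases the unbounded N downward. For assumed means of 0.06-0.12 per week and CV 0.5-0.8 the understatement is about 5-10 points. About 2-3 of those points belong to the dropout-hazard calculation, and the whole is smaller if a minimum rate applies.

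N_t is unaffected when the need is below 200 or when both values exceed 240. It can be roughly 5-30 patients too low (34 in the worst row tabulated at 0.06 per week) when the interim attack rate or PF2 difference is below plan. Those totals include the two side effects separated above. At 0.06 per week, true PF2 power at the chosen N_t would be about 79-82% rather than 85%. The documents give no attack rate and no spread, and the decision flowchart is not shown, so these are scenario values and not estimates for this trial.

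**What to change.** Draw each simulated patient's weekly rate from a gamma-Poisson (negative binomial) model fitted to attacks and weeks per interim patient, or resample interim patients. For patients already enrolled, condition the rate on their own history. State in Appendix I that the attack count includes training attacks and that patient-weeks stop at exit from Stage 1. Carry the distribution of study attacks per patient into the power calculation, not only its mean.

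The cost is a few more lines in the simulation; the per-patient data are already in the interim data set. The drawback is that the spread is estimated from limited interim data, so the projection should be shown over a plausible range of it.

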# 1.4 Interim analysis procedure

After 60 subjects have provided data from at least one study attack in Stage 1, an interim analysis (IA) will be conducted. The IA will include all reported study attacks according to the ITT principle (see section 1.6 below).

Based on the data from the IA it will be decided how many additional patients to recruit into the study, and in turn how many patients will be included in total (N\_t). This decision will be taken according to the decision procedure flowchart shown in Figure 1:

[figure not shown]

Figure 1: Interim Analysis decision procedure

As shown in Figure 1, the interim analysis performs hypothesis tests for AMSP2 and PF2, using the O'Brien Fleming Spending function in which the significance thresholds of the p-value are respectively 0.0052 at the interim analysis and 0.048 in the full analysis.

The interim analysis will use the following assumptions:

- The observed AMSP2 and PF2 at the interim for both treatment arms
- The observed Intraclass Correlation based on the interim data set
- The number of attacks per patient in the full data set will be estimated via a simulation using as its input the attack frequency observed in in the interim data set (see Appendix for details).
- The dropout percentage in the full data set will be estimated via a simulation using as its input the risk of dropout in a given week during the interim period (see Appendix I for details).

As shown, the total number of included participants will be capped at 240 since this is the largest study that will be feasible to conduct.

The interim analysis does not include a criterion for early stopping due to effectiveness.

Staff involved in the conduct of the trial and closing enrolment will remain blind to the exact result of the interim analysis, but will be informed of the final enrolment target (N\_t). Study site staff will remain blind to the exact result of the interim analysis and final enrolment target (N\_t).

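### SAP Appendix I divides exits before the first study attack by all patient-weeks, so the interim projection can understate dropout and leave N_t a few patients short

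*SAP*

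**What the plan says.** SAP 1.4 lists the dropout percentage among the inputs to the interim re-estimation and refers to Appendix I for the method.

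- **Definition (Appendix I, 2.1).** N_DO counts participants with no study attack by the end of Stage 1, in two parts. Intentional dropouts are those who left or were exited and "who by the time of dropout has NOT reported at least one study attack". Passive dropouts are still in the study but have no study attack when Stage 1 closes. Of participants who leave after a study attack, the SAP says "these patients will not count in the dropout percentage since they do contribute data to the end point analysis".
- **Input (Step 1).** The weekly dropout likelihood is "the total number of intentional dropouts in the interim data set, divided by the summed number of patient weeks in study". The weeks are not restricted.
- **Use (Simulation step).** Going forward from the interim, the instruction is to "simulate occurrences of dropout and attack reports for each patient, according to the likelihoods in the interim data set".
- **Frame.** The interim takes place "After 60 subjects have provided data from at least one study attack in Stage 1" (SAP 1.4). On size, "The clinical investigation will randomize at minimum 200 participants and at maximum 240" (SAP 1.2).

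**The concern.** The numerator and denominator describe different risk sets. Under 2.1, only a participant without a study attack can become an intentional dropout. The first treated attack is a training attack, so the at-risk period ends at the second reported attack. Participants then stay in Stage 1 until their fourth, and those later weeks enter the denominator but can add nothing to the numerator. The resulting rate is applied to every patient, including those still waiting for a first study attack, for whom it is too low.

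The weekly rate feeds the projected number of evaluable participants and hence N_t. What is at stake is power for PF2, the endpoint that drives the sizing. SAP Table 1 gives AMSP2 99.1% power at 200, so the primary endpoint has ample margin.

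**Working it through.** **1. The plan's own figure.** SAP Table 1 pairs 136 evaluable participants with a total N of 200 at 32% loss: 136/(1 − 0.32) = 200.0, which reproduces exactly. For power at 136 evaluable, the size-weighted mean cluster is (1+4+9)/(1+2+3) = 2.333 and the design effect is 1 + 1.333 × 0.486 = 1.648. At two-sided 0.048 this gives 81.1% for PF2 and 99.7% for AMSP2, against 85.5% and 99.1% in the table. Simulating the adjusted test gives 82.3% or 84.4% for PF2, depending on how the ICC is read. That difference does not bear on this point.

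**2. Direction.** Let D_pre be exits before the first study attack, and T_pre and T_post the Stage 1 weeks before and after it.

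- Written rate: D_pre/(T_pre + T_post)
- At-risk rate: D_pre/T_pre
- Ratio: T_pre/(T_pre + T_post), below 1 whenever T_post > 0

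T_post cannot be negligible when 60 participants already have a study attack. As a rough bound, take 0.10 attacks and a 1.2% exit hazard per week with complete follow-up. The chance of reaching the second attack is about (0.10/0.112)² = 0.80, so T_post is about 0.80 × T_pre and the ratio about 1/1.80 = 0.56. At the interim many participants are recent, so the ratio should be somewhat higher.

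**3. Size.** The documents give no interim rates, so these are assumptions. The eligibility floor of 3 attacks in six months (Protocol 12.1.1) is 3/26 = 0.115 per week. Appendix I was run week by week: N = 200, interim at 60 participants with a study attack, exit at four attacks, 26 weeks after last patient in (Protocol 10.3.1), constant hazard, 300 runs per row. Matched means D_pre/T_pre before the first study attack and a separate rate after it. The last column is 210 × (1 − written share)/(1 − matched share).

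| Attacks/week | Exit hazard | Accrual (weeks) | Written / at-risk rate | No-data share: written | Matched | Simulated truth | N if written gives 210 |
|---|---|---|---|---|---|---|---|
| 0.08 | 0.009 | 100 | 0.0064/0.0091 = 0.70 | 20.8% | 23.3% | 23.0% | 217 |
| 0.115 | 0.015 | 100 | 0.0098/0.0147 = 0.67 | 19.1% | 22.7% | 22.9% | 220 |
| 0.06 | 0.009 | 100 | 0.0065/0.0089 = 0.73 | 29.0% | 30.6% | 30.9% | 215 |
| 0.115 | 0.015 | 39 | 0.0114/0.0148 = 0.77 | 22.4% | 24.4% | 24.0% | 216 |
| 0.08 | 0.009 | 39 | 0.0072/0.0089 = 0.81 | 26.7% | 27.7% | 27.7% | 213 |

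With 0.10 attacks per week and a hazard of 1.2%, the written method projected 19.2% against 22.0% true: (1 − 0.192)/(1 − 0.220) = 1.036, or about 7 patients at N = 200. Over attack rates of 0.06-0.30 and hazards of 0.004-0.015 per week, the rate ratio was about 0.55-0.8 and the understatement about 0.6-4 points.

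**4. Effect on N_t.** Take the planning requirement of 136 evaluable and add the SAP's 10% missing attacks as SAP 1.5.1 does. The written share gives 136/(1 − 0.192 − 0.10) = 192; the true share gives 136/(1 − 0.220 − 0.10) = 200. Both lead to the floor of 200, so N_t does not change. Only a requirement inside 200-240 moves it, by about 3-10 patients. Table 1 gains 1.6 points of PF2 power from 190 to 200 (83.9% to 85.5%), and the calculation in step 1 just under 2 points per ten patients.

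**5. Departures from a constant hazard.** With exits concentrated in the first eight weeks, the written method gave 21.3% against 20.8% true in one case and 17.6% against 18.9% in another. The matched rate overshot in both (23.9% and 21.3%).

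**The case against.** - **Step 1 may mean all exits.** It labels the quantity as the chance of leaving or being exited in a given week, and intentional may only mean active rather than passive. All patient-weeks would then be the right denominator, and under a constant hazard the projection is sound (22.8% against 23.0% true in the first row's scenario). This is the strongest defence, but 2.1 defines the term narrowly and Step 1 uses that term. The text needs correcting on either reading.
- **A reader might infer a much larger shortfall.** Applying the low rate to the whole trial can suggest 15.2% without data against 21.4%, and N about 8% too small. Appendix I does not work that way. It projects forward from the interim, so dropouts already observed are kept, and some missed intentional dropouts return as passive ones. The size is roughly halved.
- **A reader might infer that final N will be too low.** The documents do not show this. N_t is bounded at 200 and 240, and the mapping from dropout to N_t is in SAP Figure 1, which was not available in the text reviewed. The sign also depends on the timing of exits.
- **A reader might infer that the dropout count is zero.** SAP 1.4 runs the interim on the ITT principle, and SAP 1.6.1 limits ITT to participants with a study attack. That would make the Step 1 input meaningless, so it is unlikely to be intended. A clarifying phrase is enough.
- **There is a partial offset.** If exits stop after the first study attack, the written rate also projects too few later attacks (2.74 against 2.89 per patient), which pushes N up.

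**Conclusion.** The mismatch between definition and formula is real, and under a roughly constant exit hazard it biases projected dropout downward. At assumed rates of 0.08-0.15 attacks and 0.8-1.2% exits per week, the weekly rate is about 0.6-0.7 of the at-risk rate and the no-data share is about 2-3 points too low. The consequence is conditional: N_t can be about 3-10 patients short, worth up to about 2 points of PF2 power, if the re-estimated N lies within the 40-patient window. Otherwise N_t is unaffected. The point is worth correcting because a stated rule gives a wrong input to a sample-size decision, but it does not threaten the primary analysis.

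**What to change.** Reword Step 1 to use all randomised participants and Stage 1 weeks only, by one of two routes:

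1. Divide exits before the first study attack by patient-weeks before the first study attack, and estimate a separate exit rate for later weeks to project attacks per patient.
2. Divide all exits by all Stage 1 patient-weeks and apply that rate to every patient. N_DO is still counted at the end as 2.1 defines it.

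The two agree under a constant hazard. They diverge otherwise: with no exits after the first study attack, route 2 gave 19.3% against 23.1% true and route 1 gave 23.0%; in the two early-exit cases route 2 was closer (21.8% against 20.8% true, 18.5% against 18.9%). Tabulating interim exits by time since enrolment would show which suits. Neither route corrects for attack rates that differ between patients: in one such run the matched rate gave 23.8% against 31.0% true.

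No new data are needed. The cost is a short change to Appendix I and its spreadsheet, plus the submission to the Competent Authorities that SAP 1.7.3 requires for SAP changes.
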